## Our related studies

We have developed a novel acupuncture mode called comprehensive acupuncture therapy (CAT). CAT was built up from “dense cranial electroacupuncture stimulation (DCEAS)”, which consists of dense frontal acupoints with additional electrical stimulation, together with manual stimulation of multiple body acupoints selected based on previous clinical trials, the experience of acupuncture experts, and traditional Chinese Medicine (TCM) theory on the elderly’s constitutions. The efficacy of CAT has been well proven in our previous studies. Most recently, we have completed three clinical trials that evaluated the efficacy of acupuncture treatment for vascular dementia; stroke-caused cognitive deterioration, and chemotherapy-induced cognitive impairment. All these trials have consistently revealed that acupuncture is effective in alleviating cognitive impairment. Furthermore, our several studies have confirmed the efficacy of acupuncture in improving major depression; insomnia and anxiety; poststroke depression and movement disability.

Acupressure is a form of massage therapy involving the application of pressure to acupoints or specific body surfaces. We have developed a caregiver-performed acupressure protocol called ‘Comfy Acupressure for the Elderly (CAE)’ and a demonstration video is accessible at <https://www.youtube.com/watch?v=pAqNIZPKmnM>. CAE protocol was initially developed based on traditional Chinese Medicine theory and practice, with the aim of improving the quality of life and preventing aging and age-related conditions in the elderly. We have also shown the effectiveness of caregiver-performed acupressure on the general quality of life in frail older people, and self-administered acupressure for insomnia disorder.

These studies have led us to hypothesize that (1) CAT and CAE monotherapy could reduce cognitive impairment and related comorbid symptoms in aged people with dementia; and (2) CAT and CAE as a holistic intervention could produce additive effects than routine care in improving cognitive impairment, frailty-related disability and dependency, as well as comorbid symptoms in elderly people with dementia.

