Statistical Analysis Plan

Combining acupuncture and acupressure for dementia elderly: an assessor-blinded, randomized controlled trial

Affiliated institution:

School of Chinese Medicine, LKS Faculty of Medicine, The University of Hong Kong

Principal Investigator

[name], PhD

School of Chinese Medicine, LKS Faculty of Medicine, The University of Hong Kong

Tel no.: [name]

E-mail: [contact]

Abbreviations

Abbreviations: CAT, comprehensive acupuncture therapy; CAE, Comfy Acupressure for the Elderly; DSF, Digit Span Forward; DSR, Digit Span Reverse; MoCA, Montreal Cognitive Assessment; MBI, Modified Barthel Index; VAS, Visual Analogue Scale; GDS, Geriatric Depression Scale; ISI, Insomnia Severity Index.

Last edited and approved: 21 August 2020

Introduction

This statistical analysis plan (SAP) describes the planned analyses to be performed on data collected in the clinical trial titled “Combining acupuncture and acupressure for dementia elderly: an assessor-blinded, randomized controlled trial”. No statistical analyses will be performed until the final version of this SAP has been approved.

Study design

It is an assessor-blinded, randomized controlled trial. A total of 248 eligible subjects will be recruited from local nursing and care homes. They will be randomly assigned to either an acupuncture group (named the “comprehensive acupuncture therapy [CAT]” group), an acupressure group (named the “Comfy Acupressure for the Elderly [CAE]” group), a combined acupuncture and acupressure group (named the CAT+CAE group), or a control group (named the routine care group), with 62 subjects per group. Subjects assigned to the CAT, CAE, and CAT+CAE groups will respectively receive 2 sessions of CAT, 3 sessions of CAE, and a combination of both per week for 12 weeks.

Hypothesis and aims

The hypotheses of this trial are:

- (a) acupuncture, acupressure, and their combination are feasible, safe, and could produce better management outcomes than routine care for the elderly with cognitive impairment or dementia; and
- (b) combining acupressure and acupuncture as a holistic intervention could even produce additive and even synergistic effects over their monotherapies.

The aims of this study are:

- (a) to determine whether the condition of cognitive impairment in the treatment group improves significantly when compared to the control;

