Our recent study showed that CAT treatment for 8 weeks produced a 2.3 ± 2.8 (SD) score greater improvement than control (minimum acupuncture stimulation, MAS) on MoCA in patients with poststroke cognitive impairment.¹³ One similar trial has reported that acupuncture treatment alone for 3 months yielded a 1.9 ± 4.1 greater improvement than nimodipine, a commonly used anti-hypertension drug, on MoCA in patients with poststroke cognitive impairment.¹⁴ Based on these two trials, we expect that CAT could yield an average 2.1 [$(2.3+1.9)/2 = 2.1$] score greater improvement on MoCA than routine care, with an average standard deviation (SD) equal to a 1.7-fold of mean difference [$(2.8/2.3 + 4.1/1.9)/2 = 1.7$], i.e., $SD = 1.7 \times 2.1 = 3.6$. The following formula is then used to further calculate the sample size:

$$n = \frac{2}{(M/SD)^2} \times C_{p,\text{power}}$$

where n is the number of subjects required in each arm and M is the mean difference that is equal to 2.1. SD is the standard deviation that is 3.6. $C_{p,\text{power}}$ is equal to 7.9 when the two-tailed level of α and power ($1-\beta$) are set at 0.05 and 80%, respectively. It requires 62 subjects per arm, with an assumed dropout rate of 25%. We propose to recruit a total of 248 subjects ($n = 62$ per arm for 4 arms).

Data processing and analysis

General principles

One biostatistician who is blinded to interventions will be responsible for statistical analysis. The analysis will be carried out on the intention-to-treat (ITT) population. For all primary and secondary outcomes, two-tailed P-values will be reported in addition to confidence intervals. The nominal level of statistical significance (α) will be 5%. The analysis and reporting of the results will follow the Consolidated Standards of Reporting Trials (CONSORT) guidelines.

Analysis software

All analyses will be performed using R Studio version 4.0.0 or later.

Analysis Populations

All analyses will be carried out on the intention-to-treat (ITT) population, for which participants have been randomized, completed the baseline assessment regardless of protocol compliance.¹⁵ The flow of patients throughout the trial will be shown using a CONSORT diagram (Figure 1).

Demographic characteristics and baseline comparisons

Baseline comparisons will be tabulated for the following variables (Proposed Table 1):

- (a) Age
- (b) Gender (Categories: male / female)

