- (c) Marital status (Categories: married or living with partner / single, separated, divorced, or widowed)
- (d) Education level (Categories: uneducated / primary or below / lower secondary / upper secondary / university or above)
- (e) Past occupation (Categories: managers and administrators / professional and associate professional / skilled and semi-skilled worker / unskilled worker / housework / others)
- (f) Type of cognitive impairment (Categories: Alzheimer's disease / vascular dementia / others)
- (g) Past medical history (Categories: cardiometabolic disease / malignant neoplasm / stroke / Parkinson's disease / psychotic disorder / affective disorder)
- (h) Current medication (Categories: cholinesterase inhibitors / glutamate regulators / antidepressants / antipsychotics / hypnotics)

- (i) Baseline MoCA score
- (j) Baseline DSF and DSR scores
- (k) Baseline MBI score
- (l) Baseline VAS score
- (m) Baseline GDS-15 score
- (n) Baseline ISI score

Continuous variables will be presented using mean with standard deviation (SD). One-way analysis of variance (one-way ANOVA) will be used to detect differences in continuous baseline variables.

Categorical variables will be presented by counts with percentages. Percentages will be calculated according to the number of patients for whom data are available. Categorical variables will be analyzed using the Chi-square test or Fisher's exact test.

Discontinuation will be summarized by counts with percentages. Chi-square test or Fisher's exact test will be used to detect differences between the four groups.

Primary outcome

A linear mixed-effect model will be applied to compare the primary outcome (changes in total MoCA score from baseline), with time (baseline, week 6, and week 12) and group (CAT, CAE, CAT+CAE, and routine care) as categorical fixed factors and random intercepts within a scaled identity covariance matrix. Gender, age, baseline MoCA score, and baseline medication will serve as covariates. Pairwise comparisons will be further carried out to examine between-group differences. Two-tailed P-values will be reported in addition to confidence intervals ([Proposed Tables 2 and 3](#)).

Subgroup analysis will be further conducted to compare outcomes to detect whether these subgroup factors are associated with outcomes. The following subgroups include:

- (a) Age (<85 years and \geq 85 years);
- (b) Gender (male and female); and

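### The four arms form a complete 2x2, but the SAP plans only pairwise contrasts: the two estimates of each treatment's effect are never combined, and no contrast addresses additivity or synergy

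*SAP*

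**What the plan says.** Allocation is 1:1:1:1 (SAP, Randomization, central allocation and blindness). All four groups continue routine care, and the combined group receives both regimens as they are given singly (SAP, Intervention). The arms are therefore CAT yes/no crossed with CAE yes/no.

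The primary analysis is a mixed model in which group is one categorical factor with four levels. It continues: "Pairwise comparisons will be further carried out to examine between-group differences" (SAP, Primary outcome). Proposed Table 2 lists the six pairs at Weeks 6 and 12, each with a difference, 95% CI and P value. Neither document specifies a CAT main effect, a CAE main effect or a CAT-by-CAE interaction.

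On the combination, the protocol expects that "CAT and CAE as a holistic intervention could produce additive effects than routine care" (Our related studies). SAP hypothesis (b) says that combining the two "could even produce additive and even synergistic effects over their monotherapies" (Hypothesis and aims).

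The sample size is set for one pair, CAT vs routine care: "M is the mean difference that is equal to 2.1" and "SD is the standard deviation that is 3.6" (SAP, Sample size determination). Both trials behind these figures are acupuncture trials.

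**The concern.** In a 2x2 layout two contrasts estimate the effect of CAT: CAT minus routine care (CAE absent) and CAT+CAE minus CAE (CAE present). The same holds for CAE. If effects add, both contrasts in each set estimate the same quantity, and their average has half the variance of either one. The plan reports them side by side and stops there.

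Two things are at stake. The first is precision for CAE, which has no MoCA effect size in the sample-size section. If its true effect is below the 2.1 points assumed for CAT, the CAE vs routine care contrast has less than the planned power.

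The second is SAP hypothesis (b). CAT+CAE vs CAT and CAT+CAE vs CAE show whether the combination beats each monotherapy, but not whether the effects are additive, more than additive or less. Under exact additivity CAT+CAE vs CAE simply equals the CAT effect, so a positive result there says nothing about synergy. The contrast that does, the interaction, is not in the plan.

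**Working it through.** **Inputs** (SAP, Sample size determination): difference 2.1, SD 3.6, two-sided alpha 0.05, power 80%, multiplier 7.9, 25% dropout, 62 per arm. Completers per arm: 62 x 0.75 = 46.5.

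**The plan's own figure.** n = 2/(2.1/3.6)² x 7.9 = 46.43, and 46.43/0.75 = 61.9, i.e. 62 per arm. The stated sample size reproduces.

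**Standard errors**, with n = 46.5 per arm:
- One pair: 3.6 x √(2/46.5) = 0.747
- Marginal effect (average of two simple effects, 93 vs 93): 3.6 x √(2/93) = 0.528
- Interaction (CAT+CAE - CAT - CAE + routine care): 3.6 x √(4/46.5) = 1.056

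The marginal SE is 1/√2 = 0.71 of the pairwise SE, about 29% smaller.

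**Difference detectable with 80% power** (SE x 2.80, where 2.80 = 1.96 + 0.84): 2.09 for a pair, 1.48 for a marginal effect and 2.96 for the interaction.

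**Power with no interaction** (noncentral t, 46 vs 46 for a pair and 92 vs 92 for a marginal effect):

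| True effect | Pairwise | Marginal |
|---|---|---|
| 1.0 | 26% | 47% |
| 1.5 | 51% | 80% |
| 2.1 | 79% | 98% |

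The normal approximation with 46.5 per arm gives 80.3% and 97.8% in the last row.

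**If the effects interact.** Let g be the interaction in MoCA points. The documents give no value, so the range is assumed. The marginal contrast then estimates the monotherapy effect plus g/2. For a monotherapy effect of 2.1 (normal approximation, pairwise power 80.3%):

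| g | Marginal contrast estimates | Power |
|---|---|---|
| -2.1 | 1.05 | 51% |
| -1.05 | 1.575 | 85% |
| 0 | 2.1 | 98% |
| +2.1 | 3.15 | >99% |

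Break-even is where (2.1 + g/2)/0.528 = 2.1/0.747, so 2.1 + g/2 = 1.485 and g = -1.23. In general it is -0.586 times the effect: -0.88 for 1.5 points and -0.59 for 1.0.

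**Can the trial check additivity?** Power for an interaction of 2.1 points: 2.1/1.056 = 1.99, and Φ(1.99 - 1.96) = 51%. For an interaction of 1.05 points it is 17%.

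**The case against.** The pairwise analysis has a sound defence. The SAP's first hypothesis sets each treatment, alone or combined, against routine care. The sample size is built for one such contrast and reproduces. Analysing a 2x2 as four arms is a recognised choice that stays valid whatever the interaction. All of this stands, and it is why the pairwise contrasts should remain.

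There is also reason to doubt exact additivity. CAT and CAE share stimulated points: Taiyang, Hegu and Yintang appear in both the CAT acupoint list and the CAE procedure (Protocol, Treatment procedure and Tables 1 and 2). An effect less than additive is plausible, and then the marginal estimate is pulled below the monotherapy effect. This also stands. It limits how the marginal effects may be read but does not remove the case for reporting them with the interaction.

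A reader might infer that half the data on each treatment goes unused. The documents do not support that: all four arms enter one model, and Table 2 reports both simple effects of each treatment. The data are used but not combined.

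A reader might also infer that the plan assumes additivity and so contradicts itself by not pooling. The protocol's wording is loose, and the SAP allows synergy as well. Neither document states a no-interaction assumption.

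**Conclusion.** The point holds as a gap in the planned contrasts, not as an error in the primary analysis. Under additivity the marginal effects would lower the detectable difference from 2.1 to 1.5 MoCA points at no cost in patients, and a hypothesis stated in the SAP has no contrast that addresses it.

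The figures assume a common SD of 3.6, 46.5 completers in each arm, independent participants and an unadjusted two-sided 5% level. The ratio between the two SEs needs only equal arm sizes and a common variance. The power gain needs an interaction near zero or positive. With a positive interaction the marginal effect is larger than the monotherapy effect, so it answers a different question.

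Two further inferences go too far. One is that a CAE effect below 2.1 points would probably be missed: pairwise power is still about even at 1.5 points (51%) and higher between there and 2.1. It falls clearly below one half only for smaller effects, such as 26% at 1.0. The other is that a non-significant interaction would license the marginal effects as the main result. With an SE of 1.06, the interaction estimate cannot establish additivity.

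**What to change.** Keep the six pairwise contrasts as planned. Add to the SAP, for Week 12 from the same model and labelled supporting, each with a 95% CI:

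1. Marginal CAT effect: the average of (CAT - routine care) and (CAT+CAE - CAE).
2. Marginal CAE effect: the average of (CAE - routine care) and (CAT+CAE - CAT).
3. Interaction: CAT+CAE - CAT - CAE + routine care.

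Print them beside the pairs in Table 2. State that each marginal effect averages over presence and absence of the other treatment (monotherapy effect plus half the interaction), that it must be read with contrast 3 and its interval, that a non-significant interaction does not show additivity, and that these estimates do not replace the pairwise conclusions.

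The cost is three linear contrasts and a few lines of text, with no new patients, visits or data. The downside is three more estimates beside six pairs that are already tested at a nominal 5%, which is why the supporting label matters. Make the change as a dated amendment before unblinding; if added later, the contrasts should be reported as post hoc.

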### **Data processing and analysis**

One biostatistician who is blinded to interventions will be responsible for statistical analysis. The analysis will be carried out on the intention-to-treat (ITT) population, for which participants have been randomized. A linear mixed-effect model will be applied to compare the primary outcome (changes in total MoCA score from baseline) and secondary outcomes (changes in scores of the Digit span test, MBI, VAS, GDS and ISI), with time (baseline, week 6, and week 12) and group (CAT, CAE, CAT+CAE, and routine care) as categorical fixed factors and random intercepts within a scaled identity covariance matrix. Gender, age, baseline MoCA score, and baseline medication will serve as covariates. Subgroup analysis will be further conducted to compare outcomes by gender, age, and severity of dementia to detect whether these factors are associated with the outcomes. Pairwise comparisons will be further carried out to examine between-group differences. One-way analysis of variance (one-way ANOVA) will be used to detect differences in continuous baseline variables. Categorical baseline variables, including discontinuation and incidence of AEs, will be analyzed using the Chi-square test or Fisher's exact test. Statistical significance was defined as a two-tailed  $P < 0.05$ . The analysis will be conducted using R Studio software.

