- (c) severity of dementia (mild cognitive decline [Stage 3], moderate cognitive decline [Stage 4], moderately severe cognitive decline [Stage 5])

Secondary outcomes

A linear mixed-effect model will be applied to compare the secondary outcomes, including changes in scores of the Digit span test (DSF and DSR), MBI, VAS, GDS and ISI, with time (baseline, week 6, and week 12) and group (CAT, CAE, CAT+CAE, and routine care) as categorical fixed factors and random intercepts within a scaled identity covariance matrix. Gender, age, baseline MoCA score, and baseline medication will serve as covariates.

Pairwise comparisons will be further carried out to examine between-group differences. Two-tailed P-values will be reported in addition to confidence intervals ([Proposed Tables 2 and 3](#)).

Safety outcomes

AEs related to treatment will be tabulated by treatment group without statistical tests or confidence intervals ([Proposed Table 4](#)).

All AEs that occurred throughout the trial will be tabulated by treatment group and AE category (mild, moderate, severe, life-threatening, or death). Chi-square test or Fisher's exact test will be used to detect differences between the four groups ([Proposed Table 5](#)).

Details of serious AEs and death cases will be summarized and listed in a separate table.

Interim analysis

No interim outcome analyses were done prior to the completion of the study to avoid assessment bias.

Missing data

A linear mixed-effect model will be conducted for all analyses of primary and secondary outcomes without imputation of missing data.¹⁶

Proposed Tables

Table 1. Baseline characteristics

Characteristic	CAT (n=62)	CAE (n=62)	CAT+CAE (n=62)	Routine care (n=62)	Total (n=248)	P value
Age, years *	XX ± XX	XX ± XX	XX ± XX	XX ± XX	XX ± XX	XX
Gender (Female) †	XX (XX)	XX (XX)	XX (XX)	XX (XX)	XX (XX)	XX
Marital status †						XX
Married or living with partner	XX (XX)	XX (XX)	XX (XX)	XX (XX)	XX (XX)	
Single, separated, divorced, or widowed	XX (XX)	XX (XX)	XX (XX)	XX (XX)	XX (XX)	
Education level †						XX
Uneducated	XX (XX)	XX (XX)	XX (XX)	XX (XX)	XX (XX)	
Primary or below	XX (XX)	XX (XX)	XX (XX)	XX (XX)	XX (XX)	
Lower Secondary	XX (XX)	XX (XX)	XX (XX)	XX (XX)	XX (XX)	
Upper Secondary	XX (XX)	XX (XX)	XX (XX)	XX (XX)	XX (XX)	
University or above	XX (XX)	XX (XX)	XX (XX)	XX (XX)	XX (XX)	
Past occupation †						XX
Managers and administrators	XX (XX)	XX (XX)	XX (XX)	XX (XX)	XX (XX)	

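### The subgroup analysis is described as a search for association with the outcome, and no treatment-by-subgroup interaction is planned, so nothing in it tests whether the treatment effect differs by age, gender or dementia stage

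*SAP*

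**What the plan says.** In the SAP, the subgroup analysis appears under Data processing and analysis, Primary outcome. Its purpose is "Subgroup analysis will be further conducted to compare outcomes to detect whether these subgroup factors are associated with outcomes". The factors are age cut at 85 years, "Gender (male and female"), and "severity of dementia (mild cognitive decline [Stage 3], moderate cognitive decline [Stage 4], moderately severe cognitive decline [Stage 5"]). The protocol, under Data processing and analysis, plans "to compare outcomes by gender, age, and severity of dementia to detect whether these factors are associated with the outcomes".

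The SAP's primary model is a linear mixed-effect model "with time (baseline, week 6, and week 12) and group (CAT, CAE, CAT+CAE, and routine care) as categorical fixed factors". It adds: "Gender, age, baseline MoCA score, and baseline medication will serve as covariates". Age and gender are therefore already main effects in that model. Dementia stage is not.

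Under General principles the SAP sets a single threshold: "The nominal level of statistical significance (α) will be 5"%. The footnotes to proposed Tables 2 and 3 put results below 0.05 in bold. None of the five proposed tables reports subgroup results. Neither document mentions an interaction of treatment with a subgroup factor, an exploratory label, or a rule for reading several subgroup results together.

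**The concern.** Whether older residents, or those at a later stage, have different MoCA changes is a question about prognosis. The usual reason for a subgroup analysis in a randomised trial is to ask whether the difference between arms depends on the factor. The stated purpose is the first question, and no planned term addresses the second.

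The sentence leaves two readings. Taken literally, it is a prognostic analysis. For age and gender that largely repeats what the primary model already estimates; for stage it would add something new, but still nothing about effect modification. If comparing outcomes means comparing arms inside each stratum, the only yardstick given is P<0.05. The likely output is then a significant result in one stratum and a non-significant one in another, which is not evidence that the effects differ. What is at stake is a possible conclusion that acupuncture or acupressure suits one age, sex or severity group and not another when the effect is the same in all of them.

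**Working it through.** **Inputs.** From the SAP's Sample size determination (identical in the protocol): difference M = 2.1, SD = 3.6, two-sided alpha 0.05, power 80%, constant 7.9, dropout 25%, 62 per arm. The M of 2.1 is the planning figure for CAT; the documents give none for CAE or CAT+CAE. Subgroup shares are not in the documents, so I assume 50/50, 70/30 and 80/20 for a two-level factor and equal thirds for stage.

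**The plan's own figure.** n = 2/(M/SD)² × 7.9 = 2/(2.1/3.6)² × 7.9 = 46.43. Dividing by 0.75 gives 61.9, so 62 per arm reproduces. Evaluable per arm: 62 × 0.75 = 46.5.

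**Separate tests within strata, same true effect of 2.1 in every stratum.** I used two-sample t-test power for one active arm against routine care at one time point. Strata contain different residents, so their results are independent. With two strata of power p1 and p2, the chance that exactly one is significant is p1(1−p2) + p2(1−p1). With three strata of equal power p, the chance of a mixed result is 1 − p³ − (1−p)³.

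| Split, 46.5 per arm | Power in each stratum | Chance of a mixed result |
|---|---|---|
| 50/50 (23.25 each) | 0.494, 0.494 | 0.500 |
| 70/30 | 0.640, 0.317 | 0.551 |
| 80/20 | 0.699, 0.220 | 0.611 |
| Equal thirds (15.5 each) | 0.349 each | 0.681 |

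For the thirds: 1 − 0.349³ − 0.651³ = 1 − 0.043 − 0.276 = 0.681.

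With no dropout (62 per arm) the four chances are 0.47, 0.55, 0.64 and 0.74, so the result does not hinge on the dropout assumption.

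**Sensitivity to the true effect (even split, 46.5 per arm).** The expression 2p(1−p) cannot exceed 0.50 and reaches it at p = 0.5.

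| True effect in both halves | Power per half | Chance of a mixed result |
|---|---|---|
| 0 | 0.05 | 0.095 |
| 1.0 | 0.153 | 0.26 |
| 2.1 | 0.494 | 0.50 |
| 3.0 | 0.794 | 0.33 |

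The planned effect therefore sits at the maximum for an even split.

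**What an interaction test could detect.** For one active arm against routine care and a two-level factor with share f, SE = 3.6 × √(2/(n·f) + 2/(n·(1−f))). At n = 46.5 and f = 0.5 this is 3.6 × √(0.0860 + 0.0860) = 1.49. The normal-approximation power for an interaction of 2.1 points, as large as the whole planned effect, is 29% at 50/50, 25% at 70/30 and 20% at 80/20. The interaction detectable with 80% power is 2.80 × SE, or 4.2 to 5.2 points over those splits. With 62 per arm the power is 37%, 32% and 26%.

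**The case against.** The strongest reply is that no wrong test has been specified, because no test has been specified at all. The sentence is loose, follows a model for comparing arms, and is compatible with an interaction analysis even though it does not require one. The trial's stated aims include no effect-modification aim, so the question a reader expects of a subgroup analysis is partly the reader's own. The factors and the age cut-point are prespecified, which is a real strength. All of this stands.

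A reader might therefore go too far in three ways. One is to infer that the plan ties its aim to a wrong test; it names neither a test nor a subgroup model. Another is to infer that false subgroup claims will be reported; no subgroup table, within-stratum P value or subgroup claim is planned, so this is a risk and not a forecast. The third is to call the whole analysis redundant; that is largely true for age and gender but not for stage, which is not a covariate.

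The figures also need care. They apply only to the stratum-by-stratum reading, use the CAT planning effect, and ignore baseline adjustment and repeated measures, which could raise power somewhat. A mixed pattern of significance is not itself a false claim, so it should not be set directly against the 5% error rate of an interaction test. That 5% is also per test: across three factors, the chance of at least one false positive is 1 − 0.95³ = 14% if the tests are independent.

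What survives is that both documents state the same prognostic purpose, and on neither reading does the plan test whether the treatment effect differs.

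**Conclusion.** The concern holds as a cheap improvement to the plan. The wording would let an analyst follow it fully and still have no evidence on effect modification. If arms were compared separately within strata and the true effect were the planned 2.1 points throughout, a mixed pattern would appear with probability of about 50% (even split), 55% (70/30) or 68% (three equal stages). This rests on assumed subgroup shares, 46.5 evaluable per arm, the CAT planning effect, and a two-arm t-test at one time. For an even split the figure ranges from about 10% with no effect to a ceiling of 50%, so it should be quoted as conditional. I am confident that no interaction test is planned; how the analysis would actually be run or reported cannot be known from the documents.

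**What to change.** Restate the purpose in the SAP and the protocol as assessing whether the treatment effect on MoCA differs by age, gender and dementia stage. Then specify:

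- For each factor in turn, fit a full-sample model with group, time, subgroup, all two-way interactions and the group-by-time-by-subgroup term. For age, state whether the two-level factor replaces continuous age.
- Report the joint test that the week-12 arm differences are equal across subgroups. With four arms this has (4−1)×(2−1) = 3 degrees of freedom for age or gender and (4−1)×(3−1) = 6 for stage.
- Report the week-12 difference of each active arm from routine care, with 95% confidence interval, in each subgroup, and add a table shell for it.
- Label the analyses exploratory, note that no multiplicity adjustment is made across the three factors, and base no subgroup statement on within-subgroup P values.

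The cost is a short SAP paragraph, one table shell and three model fits. The drawback is low power, about 20 to 29% for one active arm against routine care on a two-level factor when the interaction is as large as the full planned effect. Most results will be inconclusive and should be reported so. Recruitment, data collection, sample size and the primary result do not change.
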